9.1 Hypothesis-driven assays based on preliminary data

We have recently developed innovative assays that will be applied to the samples in this protocol [1, 14, 15, 91]. Our preliminary data indicates that MMF treatment is associated with upregulation of expression of genes for CR3, TWEAK, FYN, IL16, IL17RA, and/or IL2RB. We will seek to confirm or refute these findings in the current study and also test for the protein expression. All except CR3 are soluble mediators and will be quantified either by a multiplex bead-based assay [14, 15] that we have optimized or by ELISA. Expression of CR3 will be measured by flow cytometry in 2 aliquots, one for total CR3 and one for activated CR3. In addition, we will use our established multiplex bead based assay for 50 soluble mediators and further characterize this population.

We will examine the early flare phenotype to determine whether this phenotype is altered in those who respond to treatment and/or whether this is a population resistant to treatment. We previously characterized this subset of lupus patients most likely to flare if treatment is not added, characterized by differential gene expression in monocyte, T cell, interferon, and inflammation modules, as well as significantly higher frequencies of activated (aCD11b+) neutrophils and monocytes, and activated (CD86hi) naïve B cells [92].

At the Screening Visit, all participants will be assigned to one of 3 consolidated clusters of phenotypes in SLE, that cover the 7 overlapping clusters we derived from gene co-expression network analysis (WGCNA) [1, 91]. Later, using more comprehensive, immunophenotyping on batched samples, we will determine whether response to MMF or MMF plus voclosporin segregates to 1 or 2 SLE immunophenotypic clusters, or whether we must look deeper at the individual immune expression modules that comprise the clusters or even at the individual gene level to characterize response to these treatments.

9.2 Exploratory Investigation of Diverse Pathologies with in SLE

We will use a structured, multi-level evaluation of the phenotypic clusters described above to establish whether the following questions can be answered:

1. Can baseline samples predict the immune factors/patterns of participants more likely to respond to MMF as a single agent versus the need to add voclosporin?
2. If some participants have a phenotype associated with high rates of response, but these individuals do not respond as expected, can interrogation of gene and protein expression patterns reveal the reason(s)? For example, can we differentiate those for whom the treatment did not meet its intended target from those for whom it did, but who may have additional pathways operating to prevent clinical improvement?
3. Will some of those latter participants have evidence of active pathways that will predict response when voclosporin is added to the regimen that would not have been present before MMF was added?

10 Biospecimen Storage

With informed consent, laboratory samples will be stored in a biorepository for future studies at OMRF. Stored samples will include serum, plasma, urine, RNA, and DNA.

11 Criteria for Participant and Study Completion and Premature Study Termination

11.1 Participant Completion

Study completion can occur in either Stage 2 or Stage 3 and the time of completion will depend on study trajectory of each participant as described in Figure 1, *Study Flow Diagram*. Completion of the study in Stage 2 can occur with either a Stage 2 Week 24 Visit where all End of Study/Safety Follow-Up assessments are conducted, a Stage 2 End of Study/Safety Follow-Up visit or an Early Termination Visit. The final study visit can follow any visit up to the Stage 2 Week 48 visit.

Completion of the study in Stage 3 can occur with either a Stage 3 End of Study/Safety Follow-Up Visit or an Early Termination Visit. The final study visit can follow any visit up to the Stage 3 Week 24 visit.

Participants who request early termination will be encouraged to return for the Safety Follow-Up Visit.

Those who cannot tolerate the study medication or develop an adverse reaction necessitating early discontinuation of the study-provided medication will continue in the study (if they agree) without receiving further study-provided medication.

11.2 Participant Stopping Rules and Early Termination Criteria

Participants may be prematurely terminated from the study for the following reasons:

1. The participant elects to withdraw consent from all future study activities, including follow-up.
2. The participant dies.
3. The DAIT Medical Monitor no longer believes participation is in the best interest of the participant.
4. The investigator no longer believes participation is in the best interest of the participant.
5. The study is stopped.
6. The participant is “lost to follow-up.”

11.3 Participant Replacement

Randomized participants who never initiate Stage 2 study treatment will not count towards the target accrual of 120.

11.4 Early Study Withdrawal

If a participant withdraws or is withdrawn from the study for any reason, they will be encouraged to return for the safety follow up visit for their final visit.

11.5 Study Stopping Rules

See Section 12.8.2.2 Ad Hoc DSMB Meetings and Section 12.8.2.2.1 Temporary Suspension of Randomization and Dosing for ad hoc DSMB Safety Review for more information on study stopping rules.

12 Safety Monitoring and Reporting

12.1 Overview

This section defines the types of safety data that will be collected under this protocol and outlines the procedures for appropriately collecting, grading, recording, and reporting those data. AEs that are classified as serious according to the definition of health authorities must be reported promptly (per Section 12.5, *Reporting of Serious Adverse Events and*

Adverse Events) to the DAIT/NIAID. Appropriate notifications will also be made to site principal investigators (PI) and the single IRB of record.

Information in this section complies with the International Conference on Harmonisation (ICH) Guideline E2A: Clinical Safety Data Management: Definitions and Standards for Expedited Reporting, ICH Guideline E-6: Guideline for Good Clinical Practice, 21CFR Parts 312 and 320, and applies the standards set forth in the National Cancer Institute (NCI), Common Terminology Criteria for Adverse Events (CTCAE), Version 5.0:

https://ctep.cancer.gov/protocoldevelopment/electronic_applications/ctc.htm#ctc_60.

12.2 Definitions

12.2.1 Adverse Event (AE)

Any untoward or unfavorable medical occurrence associated with the participant's participation in the research, whether or not considered related to the participant's participation in the research (modified from the definition of adverse events in the 1996 ICHE-6 Guidelines for Good Clinical Practice) (from OHRP "Guidance on Reviewing and Reporting Unanticipated Problems Involving Risks to Subjects or Others and Adverse Events (1/15/07)" <http://www.hhs.gov/ohrp/policy/addevntguid.html#Q2>)

12.2.2 Suspected Adverse Reaction (SAR)

Any AE for which there is a reasonable possibility that the investigational drug [or investigational study therapy regimen] caused the AE. For the purposes of safety reporting, 'reasonable possibility' means there is evidence to suggest a causal relationship between the drug and the adverse event. A suspected adverse reaction (SAR) implies a lesser degree of certainty about causality than adverse reaction, which means any adverse event caused by a drug (21 CFR 312.32(a)).

12.2.3 Unexpected Adverse Event

An AE or SAR is considered "unexpected" if it is not listed in the Investigator Brochure or package insert or is not listed at the specificity, severity or rate of occurrence that has been observed; or is not consistent with the risk information described in the general investigational plan.

12.2.4 Serious Adverse Event (SAE)

An AE or SAR is considered "serious" if, in the view of either the investigator or DAIT/NIAID, it results in any of the following outcomes (21 CFR 312.32(a)):

- a. Death.
- b. A life-threatening event: An AE or SAR is considered "life-threatening" if, in the view of either the investigator or DAIT/NIAID, its occurrence places the participant at immediate risk of death. It does not include an AE or SAR that, had it occurred in a more severe form, might have caused death.
- c. Inpatient hospitalization or prolongation of existing hospitalization.
- d. Persistent or significant incapacity or substantial disruption of the ability to conduct normal life functions.
- e. Congenital anomaly or birth defect.
- f. Important medical events that may not result in death, be life threatening, or require hospitalization may be considered serious when, based upon appropriate medical judgment, they may jeopardize the participant and may require medical or surgical intervention to prevent one of the outcomes listed above.

Elective hospitalizations or hospital admissions for the purpose of conduct of protocol mandated procedures are not to be reported as an SAE unless hospitalization is prolonged due to complications.

12.3 Grading and Attribution of Adverse Events

12.3.1 Grading Criteria

The study site will grade the severity of AEs experienced by the study participants according to the criteria set forth in the National Cancer Institute's Common Terminology Criteria for Adverse Events (CTCAE) 5.0 other than exceptions listed below. This document (referred to herein as the NCI-CTCAE manual) provides a common language to describe levels of severity, to analyze and interpret data, and to articulate the clinical significance of all AEs. The NCI-CTCAE has been reviewed by the Protocol Chair and has been deemed appropriate for the participant population to be studied in this protocol.

AEs will be graded on a scale from 1 to 5 according to the following standards in the NCI-CTCAE manual:

- Grade 1 = mild adverse event
- Grade 2 = moderate adverse event
- Grade 3 = medically significant adverse event
- Grade 4 = life-threatening or urgent intervention indicated adverse event
- Grade 5 = death

Events grade 2 or higher and all Grade 1 or higher COVID-19 events will be recorded on the appropriate AE eCRF for this study.

For grading an abnormal value or result of a clinical or laboratory evaluation (including, but not limited to, a radiograph, an ultrasound, an electrocardiogram etc.), an AE is defined as an increase in grade from screening or from the last post-screening value that doesn't meet grading criteria. If a specific event or result from a given clinical or laboratory evaluation is not included in the NCI-CTCAE manual, then an abnormal result would be considered an AE if changes in therapy or monitoring are implemented as a result of the event/result.

Liver function abnormalities will be graded using alternative criteria which are based on CTCAE version 4.0, and are defined relative to the ULN as follows:

- Aspartate aminotransferase [AST] increased
 - Grade 1: > ULN - 3.0x ULN
 - Grade 2: > 3.0x ULN - 5.0x ULN
 - Grade 3: > 5.0x ULN - 20.0x ULN
 - Grade 4: > 20.0x ULN
- Alanine aminotransferase [ALT] increased
 - Grade 1: > ULN - 3.0x ULN
 - Grade 2: > 3.0x ULN - 5.0x ULN
 - Grade 3: > 5.0x ULN - 20.0x ULN
 - Grade 4: > 20.0x ULN

- Alkaline phosphatase [ALP] increased
 - Grade 1: > ULN - 2.5x ULN
 - Grade 2: > 2.5x ULN - 5.0x ULN
 - Grade 3: > 5.0x ULN - 20.0x ULN
 - Grade 4: > 20.0x ULN
- Blood bilirubin increased
 - Grade 1: > ULN - 1.5x ULN
 - Grade 2: > 1.5x ULN - 3.0x ULN
 - Grade 3: > 3.0x ULN - 10.0x ULN
 - Grade 4: > 10.0x ULN

12.3.2 Attribution Definitions

The relationship, or attribution, of an AE to the study therapy regimen or study procedure(s) will initially be determined by the site investigator and recorded on the appropriate AE eCRF. Final determination of attribution for safety reporting will be determined by DAIT/NIAID. The relationship of an AE to study therapy regimen or procedures will be determined using the descriptors and definitions provided in Table 12.1.

For additional information and a printable version of the NCI-CTCAE manual, consult the NCI-CTCAE web site:
<http://ctep.cancer.gov/reporting/ctc.html>.

Table 12.1 Attribution of Adverse Events

Code	Descriptor	Relationship (to primary investigational product and/or other concurrent mandated study therapy or study procedure).
UNRELATED CATEGORY		
1	Unrelated	The adverse event is clearly not related; there is insufficient evidence to suggest a causal relationship.
RELATED CATEGORIES		
2	Possible	The adverse event has a reasonable possibility to be related; there is evidence to suggest a causal relationship.
3	Definite	The adverse event is clearly related.

12.4 Collection and Recording of Adverse Events

12.4.1 Collection Period

AEs will be collected from the time of consent until a participant completes study participation or until 30 days after he/she prematurely withdraws (without withdrawing consent) or is withdrawn from the study.

12.4.2 Collecting Adverse Events

AEs (including SAEs) may be discovered through any of these methods:

- Observing the participant

- Interviewing the participant [e.g. using a checklist, structured questioning, diary etc.]
- Receiving an unsolicited complaint from the participant
- In addition, an abnormal value or result from a clinical or laboratory evaluation can also indicate an AE as defined in Section 12.3, *Grading and Attribution of Adverse Events*.

12.4.3 Recording Adverse Events

Throughout the study, the investigator will record AEs and SAEs as described previously (see Section 12.2, *Definitions*) on the appropriate AE eCRF regardless of the relationship to study therapy regimen or study procedure.

Once recorded, an AE/SAE will be followed until it resolves with or without sequelae, or until the end of study participation, or until 30 days after the participant prematurely withdraws (without withdrawing consent)/or is withdrawn from the study, whichever occurs first. For AEs where an abnormal value or result of a clinical or laboratory evaluation is observed (see Section 12.3.1, *Grading Criteria*), resolution is defined as the first value post-abnormality that is in the normal range (Grade 0).

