4.3 Exclusion Criteria

Participants who meet any of the following criteria are not eligible for randomization as study participants:

1. Inability or unwillingness of a participant to understand and provide written informed consent or comply with the study protocol.
2. BILAG A (severe) disease in the Cardiorespiratory, Neuropsychiatric, Gastrointestinal, Ophthalmic, Renal, or Hematological Systems.
3. Severe or unstable nephritis defined as any of the following:
 - a. History of confirmed Class 3-5 nephritis within the last 2 years,

- b. History of confirmed Class 3-5 nephritis > 2 years ago in the absence of documented treatment including both induction and maintenance therapy,
- c. UPCR > 1 g/g at screening,
 - If UPCR is > 0.5 g/g and ≤ 1 g/g at screening, then a second assessment must be completed with at least 1 week between assessments. If the second assessment is > 1 g/g or has increased by ≥ 0.3 g/g, then the participant is excluded.

4. Evidence of chronic kidney disease defined as eGFR < 45 mL/min per 1.73 m² at screening, where $175 \times (\text{Creatinine}/88.4) - 1.154 \times (\text{Age}) - 0.203 \times (0.742 \text{ if female}) \times (1.212 \text{ if of African descent})$ [5].

5. History of cirrhosis or chronic liver disease unrelated to SLE other than fatty liver disease.

6. History, within 1 year of the Screening Visit, of uncontrolled SLE that would have warranted a BILAG A (except mucocutaneous, constitutional, musculoskeletal) including, but not limited to, hemolytic anemia, neuropsychiatric lupus, or interstitial lung disease.

7. Uncontrolled HTN at the Screening or Randomization Visits defined as a blood pressure > 150/100 with or without treatment, not to exceed 3 complementary antihypertensive treatments.

8. Any of the following laboratory values during screening:

- a. Hemoglobin (Hg) < 8.0 g/dL,
- b. WBC < 2.0 × 10⁹ cells/L,
- c. ANC < 1.0 × 10⁹ cells/L,
- d. Platelets < 60 × 10⁹ cells/L at screening,
 - If platelets < 70 × 10⁹ cells/L at screening, platelet count should be retested 2 weeks later. If platelets are < 60 × 10⁹ cells/L at retest, participant will be excluded
- e. AST or ALT > 2.5 times the ULN,
- f. Serum IgG levels < 5 g/L

9. Use of ≥ 40 mg/day of prednisone within 4 weeks prior to the Screening Visit or use of > 20 mg/day of prednisone at screening.

10. Unwilling or unable to taper to ≤ 10 mg/day of prednisone or equivalent by the day of randomization.

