6.4.9 Hematological Abnormalities

Individuals meeting thresholds for exclusionary levels of neutrophils, WBC, platelets, and hemoglobin at screening are excluded from the study (See Section 4.3, *Exclusion Criteria* number 8 for additional detail). To monitor potential hematological toxicity, the participants will have a complete blood count at each visit. If any of the following develop without explanation and persist after a repeat check in one week, then study medications will be held for one week and the test repeated:

- neutropenia (neutrophils < 800/mm³, equivalent to 0.8 x10⁹/L),
- leukopenia (WBC < 1500/mm³, equivalent to 1.5 x10⁹/L),
- thrombocytopenia (platelets < 40,000/mm³, equivalent to 40 x10⁹/L), or
- anemia (hemoglobin < 7.0 g/dL).

Study medication may be held up to 2 weeks while the abnormality is monitored weekly for recovery. If recovery to screening value occurs then study medication can be resumed. Otherwise, refer to the guidelines in Section 6.5, *Premature Discontinuation of Investigational Agent* in the event of toxicity. If participants have symptomatic complications from the hematological derangements, this should be treated according to standard of care per institutional requirements.

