6.4.10 Hepatic Abnormalities

Individuals with AST or ALT > 2.5x ULN at screening are excluded from the study. Liver function tests will be checked every 4 weeks for signs of hepatic toxicity. If transaminases exceed 3x ULN without explanation, then study medications will be held for up to 2 weeks, and the abnormality followed weekly for resolution to screening value. Should resolution occur within 14 days, the study medication may be resumed. Otherwise, refer to the guidelines in 6.5, *Premature Discontinuation of Investigational Agent* in the event of toxicity.

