13.4.4 Analyses of Secondary Safety Endpoints

Safety analyses will be performed on the safety sample and will be assessed by summarizing AEs separately for each stage of the study. The length of time participants are followed within each stage is variable and could depend on if a participant meets treatment failure. To account for potential differential duration of study participation, AE summaries by treatment group will include the number of events per person-year in addition to the number and percentage of events and participants experiencing events. AEs and SAEs will be summarized by system organ class, preferred term, and severity grade.

Safety endpoints identified in Section 3.3.2 Safety Endpoints, will be summarized and listed separately for each stage of the study. For each such endpoint, the number of events per person-year as well as numbers and percentages of events and participants who experience these events will be summarized overall in Stage 1 and by treatment group in Stage 2 and 3. No formal statistical testing will be performed to compare safety between treatment groups.

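### A laboratory adverse event in a participant who enters with a graded value opens on a rise from the screening grade but closes only at Grade 0, which can merge separate episodes and lower the event counts

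*Combined protocol and SAP*

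**What the plan says.** **Onset (12.3.1).** For clinical and laboratory values, "an AE is defined as an increase in grade from screening or from the last post-screening value that doesn't meet grading criteria". There are thus two reference points: the screening grade, and the most recent later value that is not gradable. The recording threshold is in the same section: "Events grade 2 or higher and all Grade 1 or higher COVID-19 events will be recorded on the appropriate AE eCRF".

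**End (12.4.3).** A recorded event is followed "until it resolves with or without sequelae, or until the end of study participation", or until 30 days after premature withdrawal, whichever comes first. For abnormal test values, "resolution is defined as the first value post-abnormality that is in the normal range (Grade 0". Nothing is said about a participant whose screening value was already graded.

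**Entry (4.3, criterion 8).** The transaminase exclusion is "AST or ALT > 2.5 times the ULN". The grading table in 12.3.1 puts AST and ALT above ULN and up to 3.0 times ULN in Grade 1.

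**Toxicity management (6.4.9, 6.4.10).** Recovery here is judged against the participant's own screening value. The hepatic section has "the abnormality followed weekly for resolution to screening value"; the hematological section has "If recovery to screening value occurs then study medication can be resumed".

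**Reporting (13.4.4).** Because follow-up length varies, "AE summaries by treatment group will include the number of events per person-year", along with numbers and percentages of events and of participants with events. Summaries are made separately for each stage, and safety is not formally tested between arms.

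**The concern.** The start of an event is measured from where the participant began; its end is measured against normal. For someone who began above normal, the two do not meet. A participant can be back exactly where they entered, with nothing left that the study treatment could have caused, and still carry an open adverse event.

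Three outputs depend on when an event ends. The first is its resolution status. The second is the event count: if a new rise falls inside an open event, two episodes are recorded as one, and both the number of events and the rate per person-year fall. The third is the stage an event belongs to. A participant who fails Stage 2 at or before Week 24 may be re-randomized straight away, so an event still open at that point could take in a rise that first occurs on Stage 3 treatment. The rates per person-year were chosen to allow for unequal follow-up, so the count in their numerator needs a clear rule.

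**Working it through.** The plan states no figure on this point, so there is none to reproduce. The check sets the rules side by side and applies them to example series.

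**Step 1. Can a participant enter with a graded value?** Yes. Eligible AST or ALT runs up to 2.5 × ULN, and Grade 1 runs from above ULN to 3.0 × ULN. Every eligible value above ULN is therefore Grade 1. Entry limits for blood counts are also below normal, but the protocol does not print the grade cut-offs for those tests, so the demonstration is confined to AST and ALT.

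**Step 2. Where do the rules part?**

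| Screening grade | Event opens on | Event closes at (12.4.3) | Same reference? |
|---|---|---|---|
| 0 | rise from Grade 0 | Grade 0 | yes |
| 1 | rise from Grade 1, or from a later non-gradable value | Grade 0 | no, unless the value normalizes |

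**Step 3. Apply both closing rules to ALT series.** The series are invented for illustration: one screening value and six later values, in multiples of ULN. Grades come from 12.3.1 (above 1 to 3: Grade 1; above 3 to 5: Grade 2; above 5 to 20: Grade 3). An event opens when the grade is above the screening grade and at least Grade 2. It is assumed that no new event opens while one is unresolved; the documents do not state this.

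| Series (screening; later values) | Close at Grade 0, as written | Close at Grade 0 or return to screening grade |
|---|---|---|
| 2.0; 3.5, 2.0, 2.0, 5.5, 2.0, 2.0 | 1 event, 0 resolved | 2 events, 2 resolved |
| 2.0; 3.5, 0.9, 2.0, 5.5, 0.9, 0.9 | 2 events, 2 resolved | 2 events, 2 resolved |
| 0.9; 3.5, 2.0, 2.0, 5.5, 2.0, 0.9 | 1 event, 1 resolved | 1 event, 1 resolved |
| 0.9; 3.5, 0.9, 0.9, 5.5, 0.9, 0.9 | 2 events, 2 resolved | 2 events, 2 resolved |

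Only the first series differs: a Grade 1 entrant who returns to the entry grade between rises but not to normal.

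**Step 4. Rate in the first series.** Over 24 weeks, person-years = 24 / 52.18 = 0.460. As written: 1 / 0.460 = 2.17 events per person-year. Under the alternative: 2 / 0.460 = 4.35. This is the contribution of one constructed participant, not an estimate for an arm.

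**Step 5. What does not move?** Under either rule each series has at least one event, so the within-stage percentage of participants with an event is the same. Treatment failure (3.5.1) does not refer to adverse event resolution, so the primary endpoint is untouched.

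**The case against.** The strongest reply is that no sentence forbids a new event while an earlier one is open. A second rise from Grade 1 to Grade 2 is again an increase from screening, so on a literal reading it meets the first limb of 12.3.1 a second time. This stands to the extent that merging is an inference and not a stated cap of one event per test. It does not settle the matter. An event is followed until it resolves, and the only later reference point in the onset rule is a non-gradable value; both favor treating the second rise as part of the open event. If the literal reading is taken instead, every later Grade 2 value is a rise from screening, and nothing separates continuation from recurrence.

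A reader might infer that such a participant can never resolve the event. The documents do not support that: a raised screening value can normalize on study, and the event then closes, as in the second series.

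A reader might also infer that 12.4.3 flatly contradicts 6.4.9 and 6.4.10. Those sections govern medication decisions, while 12.4.3 governs closing a record, and different purposes may justify different thresholds. They also refer to the screening value, not the screening grade. With assumed ALT of 1.2 × ULN at screening, a peak of 4 and a return to 2.8, the participant is back in Grade 1 but not at the screening value. The difference in wording needs an explanation but is not in itself an error.

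Finally, the affected outputs are descriptive, and no analysis of event duration is planned. That is correct and limits the weight of the point.

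**Conclusion.** The point holds for a limited group. Participants who enter with a graded laboratory value, shown here for AST and ALT above ULN and up to 2.5 × ULN, keep an open adverse event after returning to their entry grade unless they improve beyond it. The wrong resolution status follows directly from the text. The understated counts and rates rest on one further step, the natural but unstated reading that a rise during an open event is not a new event. Absorption of a Stage 3 rise into an event open since Stage 2 rests on the same step.

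For the illustrated participant the count is halved, from 2 to 1. No figure for an arm or for the trial can be given, because the documents state neither the share of participants entering with a graded value nor how often such rises recur. It may be tempting to say that the rule narrows a real safety difference between arms. That would need recurrence rates by arm, which are not given.

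This is a minor point: the outputs at stake are descriptive safety summaries.

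**What to change.** In 12.4.3, define resolution of a laboratory adverse event as Grade 0 or return to the screening grade or better. For a participant who screens at Grade 0 this leaves the present rule unchanged. Add that a later rise above the screening grade, including one after re-randomization, is a new event. Carry both statements into the case report form instructions.

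This concerns adverse event recording only. The sponsor should separately reconcile the screening-value wording in 6.4.9 and 6.4.10 with 12.4.3, or state that the medication decision and the closing of the record are meant to follow different standards.

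The cost is about a sentence or two of protocol text, a line of guidance for sites, and slightly more adverse event records. It is best done before records accumulate, since merged episodes are hard to separate afterwards.
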